## **6. Analytic Considerations**

### Sample size considerations

The projected sample size for the study is 1200 women enrolled from 1st ANC visit until 12-months postpartum (estimated mean of 18-months follow-up). This estimate is based on the following assumptions:

- (1) 60% of women will initiate PrEP during the study period (versus approximately 40% who will not);**
- (2) Approximately 75% of women on PrEP will be retained in care at 12-months (defined as not missing >1 study visit among women on PrEP)**
- (3) 70% of those retained in care (n=378) will adhere to PrEP during at-risk periods.**

A sample size of 1200 women yields 80% power to detect identify a relative risk of 2.0 or greater in key covariates including age (<25 vs.  $\geq$ 25 years), pregnancy and relationship status associated with PrEP initiation versus non-initiation. A sample size of 378 women (e.g. 70% of women retained in the study on PrEP will be adherent as measured by TDF-DP measures) yields 80% power to detect relative risks of 2.0 or greater associated with adherence in the cohort. The analysis will be based on women who complete the 12-month postpartum cohort follow up. We will use relative risk ratios performed at a two-sided  $\alpha$  level of 0.05.

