## Sample size considerations

The projected sample size for the study is *1200 women enrolled from 1st ANC visit until 12-months postpartum (estimated mean of 18-months follow-up)*. This estimate is based on the following assumptions:

- (1) 60% of women will initiate PrEP during the study period (versus approximately 40% who will not);
- (2) Approximately 75% of women on PrEP will be retained in care at 12-months (defined as not missing >1 study visit among women on PrEP)
- (3) 70% of those retained in care (n=378) will adhere to PrEP during at-risk periods.

A sample size of 1200 women yields 80% power to detect identify a relative risk of 2.0 or greater in key covariates including age (<25 vs. >25 years), pregnancy and relationship status associated with PrEP initiation versus non-initiation. A sample size of 378 women (e.g. 70% of women retained in the study on PrEP will be adherent as measured by TDF-DP measures) yields 80% power to detect relative risks of 2.0 or greater associated with persistence in the cohort. The analysis will be based on women who complete the 12-month postpartum cohort follow up. We will use relative risk ratios performed at a two-sided  $\alpha$  level of 0.05.

## Statistical analysis considerations for AIMS 1 & 2

The primary analysis for *Aim 1* will focus on measuring the distribution of women across the PrEP cascade including: initiation, continuation and persistence. **PrEP initiation** will be based on a woman's uptake of PrEP and allow for stoppage and re-initiation; **PrEP continuation** will be defined as not missing >1 visit among those on PrEP (with separate analyses of PrEP stoppage). For **PrEP persistence** for women on PrEP we will measure both *perfect persistence* (i.e. level of objective persistence throughout pregnancy and breastfeeding periods) as well as "*prevention-effective*" persistence (i.e. persistence during times of sexual activity) in participants through objective and subjective measures to evaluate agreement between the two measures, and the level of under- or over-reporting. Primary persistence analyses will use objective measures (TDF-DP from DBS) taken on all those who enrolled and initiated PrEP; subsidiary analyses will consider (i) other persistence measures and (ii) multiple imputation for missing persistence data.

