#### ***Methods/Approach:***

- (1) Study flow figure (see Continuation Flowcharts)
- (2) Number screened per week and month (target= 18 per week, 72 per month) vs number enrolled
  - a. The projected sample size for the study is 1200 women enrolled until 12-months postpartum (estimated mean of 18-months follow-up).
- (3) Subjects initiating PrEP compared to those who do not
  - a. Estimated that 60% of women (n=720) will initiate PrEP during the study period (versus approximately 40% who will not).
- (4) Continuation and persistence by group
  - a. Assumed that approximately 75% of women on PrEP (n=540) will continue on PrEP at 12-months (defined as not missing >1 study visit among women on PrEP);
  - b. Assumed that 70% of those retained in care (n=378) will adhere to PrEP during at-risk periods.
- (5) Final completion rates
  - a. Compare final number of participants who enroll in study, who initiate PrEP, who are retained in care, and who adhere to PrEP to sample sizes needed to yield 80% power (i.e., n=1200, 720, 540, 378, respectively).
- (6) Number of subjects in analysis data sets
  - a. Consider number of participants that will potentially be excluded from analyses because of withdrawal from study, missing data on key covariates or outcomes, etc.

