#### **Missing data:**

Primary persistence analyses will use objective measures (TDF-DP from DBS) taken on all those who enrolled and initiated PrEP; subsidiary analyses will consider (i) other persistence measures and (ii) multiple imputation for missing persistence data. Specify any sensitivity analyses. Specify how the impact of missing data on the primary results will be interpreted.

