**Interpretation:**

The analysis will be based on women who complete the 12-month postpartum cohort follow up. We will use relative risk ratios performed at a two-sided  $\alpha$  level of 0.05.

Summarize how the results will be interpreted. You can include what level of statistical significance will be used to determine the trial's main conclusion/recommendation. You can also describe how disagreement or coherence between primary and secondary results will be interpreted.

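### The 80% power for a relative risk of 2.0 does not follow from the plan's own rates, and 378 is a count of expected adherent women, not a sample size

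*Combined protocol and SAP*

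**What the plan says.** Protocol section 6 and SAP section 1, both under Sample size considerations, assume that 60% of women start PrEP, about 75% of those on PrEP are retained at 12 months, and 70% of those retained adhere. Two power statements follow, at a two-sided 5% level.

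- Initiation: "A sample size of 1200 women yields 80% power to detect identify a relative risk of 2.0 or greater in key covariates".
- Adherence (persistence in the SAP): "A sample size of 378 women (e.g. 70% of women retained in the study on PrEP will be adherent". The protocol's sentence ends "yields 80% power to detect relative risks of 2.0 or greater associated with adherence in the cohort".

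Neither document gives a covariate prevalence, a reference-group risk, a formula or software.

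SAP 2.2 shows where the numbers come from. Item (3) reads "Estimated that 60% of women (n=720) will initiate PrEP during the study period" and item (4) reads "Assumed that approximately 75% of women on PrEP (n=540) will continue on PrEP at 12-months", followed by 378 as 70% of those retained. Item (5) then asks for the final numbers to be compared "to sample sizes needed to yield 80% power (i.e., n=1200, 720, 540, 378, respectively".

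On who is analysed for persistence, SAP 2.4 (Missing data) says "Primary persistence analyses will use objective measures (TDF-DP from DBS) taken on all those who enrolled and initiated PrEP", while SAP 2.4 (Interpretation) says "The analysis will be based on women who complete the 12-month postpartum cohort follow up".

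**The concern.** Three things do not fit together.

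- A sample size for predictors of adherence must include women who do not adhere. If all 378 women are adherent, the outcome does not vary among them and no predictor can be tested.
- With outcomes as common as 60% and 70%, doubling the risk is a very large effect. It should not take hundreds of women to detect at 80% power, and for less common covariates it would require a risk above 100%.
- SAP 2.2 item (5) carries the mistake into a planned check. If 350 women turned out to be adherent, the team would report a shortfall against a power requirement, although the denominator, and so the power, might be unchanged.

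These are the plan's only power statements for predictors of initiation and persistence, which are stated aims. As written, a reader cannot tell what size of association the study can detect, or in which women.

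**Working it through.** **Origin of 378.** 1200 × 0.60 = 720; 720 × 0.75 = 540; 540 × 0.70 = 378. So 378/540 = 70% and 378/720 = 52.5%. Among retained women the comparison is 378 adherent against 162 not adherent.

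**Inputs.** From the documents: two-sided 5%, RR 2.0, 80% power, rates of 60% and 70%, and N of 1200, 720, 540 and 378. Assumed, because no share is stated: a proportion f of women in the higher-rate group, varied over a range.

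**Method.** Unadjusted two-proportion comparison, normal approximation. Hold the overall rate p at the plan's value. Then:

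- p0 = p / (1 − f + f·RR) and p1 = RR·p0
- n1 = N·f and n0 = N·(1 − f)
- SE0 = √[p(1 − p)(1/n0 + 1/n1)] and SE1 = √[p0(1 − p0)/n0 + p1(1 − p1)/n1]
- power = Φ[(p1 − p0 − 1.96·SE0)/SE1]

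**Attempt to reproduce the stated 80%, equal split (f = 0.5).**

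- Initiation, N=1200, p=0.60: p0 = 0.60/1.5 = 0.40, p1 = 0.80. SE0 = 0.0283, SE1 = 0.0258. z = (0.40 − 1.96 × 0.0283)/0.0258 = 13.3, so power is above 99.9%.
- Adherence, N=540, p=0.70: 46.7% against 93.3%, z = 11.5, power above 99.9%.
- Adherence with 378 taken literally: the same rates, z = 9.2, power above 99.9%.
- N=720 at 52.5% (non-retained women counted as non-adherent): 35% against 70%, z = 7.9, power above 99.9%.

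The total needed for 80% power at an equal split is about 45 women (60% rate), 28 (70%) or 62 (52.5%).

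**Where RR 2.0 does give 80%.**

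| N, overall rate | Share in higher-rate group | Women in lower-rate group |
|---|---|---|
| 1200, 60% | 98.3% | about 20 |
| 540, 70% | 97.4% | about 14 |
| 720, 52.5% | 96.3% | about 27 |
| 378, 70% | 96.3% | about 14 |

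**Where RR 2.0 is impossible.** p1 = 2p/(1 + f) must not exceed 1, so f must be at least 2p − 1. That is 0.20 for initiation at 60% and 0.40 for adherence at 70%.

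**What the study can detect: smallest RR at 80% power.**

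| N, overall rate | f = 10% | f = 50% | f = 90% |
|---|---|---|---|
| Initiation, 1200, 60% | 1.22 | 1.14 | 1.28 |
| Initiation, completers, 900, 60% (75% completion assumed) | 1.25 | 1.17 | 1.33 |
| Persistence, 540, 70% | 1.25 | 1.17 | 1.36 |
| Persistence, 720, 52.5% | 1.34 | 1.22 | 1.47 |

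Simulation with 40,000 runs gave 79% to 81% power at each tabulated value.

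**Other readings.** An odds ratio of 2.0 gives about 80% for N=378 at 70% when f is about 0.33–0.35 or 0.75. For N=1200 at 60% it gives 92% or more for f from 0.10 to 0.90. No single ordinary share therefore produces both statements.

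**The case against.** The strongest counter-argument is that the RR could be read on the unfavourable outcome, since the plan also studies predictors of attrition. With 30% non-adherence and N=378, RR 2.0 has 80% power at a share of about 82% or 6%; with N=540, at about 88% or 4%. On that reading RR 2.0 is also never impossible. The arithmetic is right, and it limits the table of 80% shares above to RR on initiation or adherence. It does not rescue the plan. The power sentences refer to adherence or persistence, an unbalanced share still has to be supplied, and initiation is untouched: RR 2.0 on 40% non-initiation with N=1200 still exceeds 99% for shares from 3% to 90%.

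It can also be said that the missing inputs, not the arithmetic, prevent reproduction, and that 80% could be meant as a floor. At most shares it is one. But a floor that sits at over 99.9% power across ordinary shares says nothing about what the study can detect.

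It is also fair that the primary analysis of Aim 1 is descriptive, that no treatment comparison rests on this power, and that the error is mostly conservative. This limits the seriousness. Two rows of the detectable-RR table rest on assumptions the plan does not make: 75% completion across the whole cohort, and non-retained women counted as non-adherent. They are labelled so for that reason.

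**Conclusion.** The concern holds. That 378 is an outcome count follows from the plan's own figures with no outside assumption. The 80% for RR 2.0 cannot be reproduced at any ordinary covariate share. At an equal split, power exceeds 99.9%, and the detectable RR is about 1.14 for initiation (N=1200) and 1.17 for persistence (N=540), or 1.22 with N=720 at 52.5%.

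The error generally understates power and gives no reason to change the enrolment target. That is not a blanket assurance. For RR 2.0, power is 71% at a 97% share with N=720 at 52.5%, and 71% at a 90% share for non-adherence (30%, N=540).

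All figures are for an unadjusted two-group comparison at a two-sided 5% level. They make no allowance for covariate adjustment, interactions or repeated visits, so they do not describe the planned probit and GEE models exactly. The point should be fixed; it does not threaten the study.

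**What to change.** - **Protocol section 6 and SAP section 1, Sample size considerations:** remove 378 as a sample size. Replace the two power sentences with the smallest RR detectable at 80% power, stating the assumed covariate share, overall rate, denominator and two-group method. For shares of 10% / 50% / 90% in the higher-rate group: initiation, N=1200 at 60%, about 1.22 / 1.14 / 1.28; persistence, N=540 at 70%, about 1.25 / 1.17 / 1.36, or N=720 at 52.5% with non-retained women counted as non-adherent, about 1.34 / 1.22 / 1.47. If initiation is limited to completers, use the N=900 row and state that 75% completion is an assumption. Give no figure for N=720 at 70%, because the plan states 70% only for retained women. Label all figures as unadjusted.
- **Persistence set:** say which women the power figure refers to, reconciling the all-initiators rule in SAP section 1 and SAP 2.4 (Missing data) with the completers rule in SAP section 1 and SAP 2.4 (Interpretation).
- **SAP 2.2 item (5):** relabel 1200, 720, 540 and 378 as expected cascade counts.

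The cost is text edits in three places and one decision, on the persistence set. No extra participants, new data or change of model are needed.

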### Study measures

**Under Aim 1, we will measure the following primary outcomes in the PrEP cascade defined as PrEP initiation, continuation and persistence over time in the cohort.**

1. **PrEP initiation:** # of women who initiate PrEP over time / total # of women in active cohort = proportion of women who initiate PrEP
2. **PrEP continuation:** # of women on PrEP who return for study visits (do not miss more than 1 visit) / total # of women in active cohort who are prescribed PrEP= proportion of women on PrEP who continue in PrEP study

3. **PrEP persistence:** defined as reporting taking PrEP in  $\geq 5$  out of last 7 days or  $\geq 25$  out of last 30 days (self-reported), or  $\geq 600$  fmol/punch (~7 doses/week) from DBS TDF-DP at 3rd trimester, delivery and 6 weeks postpartum (objective report)

**In addition we will measure secondary outcomes defined as continuation and persistence during periods of sexual risk.** Different levels of PrEP continuation and persistence may be needed depending on sexual risk. Our study will measure both perfect persistence (e.g. level of objective persistence throughout pregnancy and breastfeeding periods) as well as “prevention-effective” persistence among participants. We will measure persistence through objective and subjective measures to evaluate the agreement between the two measures, and the level of under- or over-reporting.

- a. **Use of PrEP will be measured via:** (i) quarterly testing of DBS to test for TDF-DP adapted from previous studies of PrEP objective measures; (ii) self-reported items that we have adapted from previous studies (including 7-day, 30-day and last visit recall questionnaires), (iii) pill counts and (iv) pharmacy refill records.
- b. **Measurement of prevention-effective execution:** Execution refers to PrEP persistence during a time when at-risk sex happens. It is calculated by: number of doses reported or recorded/number of expected doses based on HIV risk and PrEP initiation/discontinuation.
- c. **Prevention-effective continuation:** Prevention-effective continuation describes the duration of PrEP use during periods of HIV risk and references the absolute time of use during pregnancy and breastfeeding periods. We will adapt the methodology from previous PrEP studies including FEM-PrEP in SA to create a semi-ordinal composite persistence score measuring plasma TDF-DP from blood specimens collected from DBS every 3-months.
- d. **In-depth interviews (IDIs):** We recognize the need for mixed methods in this study to better understand the reasons behind the biomarkers (i.e., laboratory test results of persistence) and survey responses, including why women use (or don't) use PrEP, and contextualize sexual and substance use behaviors. We will identify key risk factors to gain information about how risk factors affect the PrEP cascade to design interventions to address those factors.
  - At study month 7 and 12 we will purposefully select 60 study participants to better understand structural (or study-related) barriers to the PrEP cascade. We will select 30 participants who initiated PrEP compared to 30 participants who did not initiate PrEP (n=15) and reported poor adherence to PrEP (n=15) to compare motivations behind PrEP initiation.
  - We will interview key informants, including health care providers and managers in each facility (N=20, n=10 per facility).
  - We will develop semi-structured interview guidelines for the trained study interviewers to use. The Study Coordinator will sit in a random sample of 10% of interviews and counseling sessions to ensure that the interviewers follow the guidelines, and re-train as necessary. Based on our prior research, we expect to hit saturation after 30 interviews per site.
  - We will use factors hypothesized in our conceptual model to be salient and the findings from the CRFs to build the interview guide for the IDIs to help build upon our understanding of the PrEP cascade and factors associated with attrition in each step.
- e. **HIV outcomes.** As part of the standard of care, all pregnant and breastfeeding women will be tested for ab and ag HIV using serial rapid HIV tests at each antenatal and postnatal care visit. In addition, PrEP-PP study staff will have a stock of rapid ab/ag HIV test kits to ensure that women get tested at each study visit.
  - a. **Seroconversion.** If a woman, infant or partner seroconverts at any point during the study, they will be referred to the clinician on duty to initiate same-day ART, following counseling about PMTCT, breastfeeding, disclosure, and ART persistence, per the SA National Protocols].
- f. **Health outcomes and adverse events.** We will collect side effects and serious adverse events in mother and infant including adverse pregnancy and birth outcomes and infant growth measures.

- g. **Infant measures.** We will collect infant HIV outcomes and birth outcomes from the infant road to health card, and will collect infant growth outcomes at each quarterly visit.

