#### **Laboratory tests in women on PrEP:**

- **Renal function (in all women on PrEP):** Blood draws for creatinine levels will be taken at baseline, 3-month follow-up and at the end of the study, as per SA HIV Clinician Guidelines [26].
  - At enrollment: women with eGFR<60ml/min will be excluded from the study
  - At 3-month follow up: Women will not be able to continue taking PrEP with an eGFR <60m/min but will be able to continue to participate in the study. If their creatinine results change at the following visit they will be eligible to start PrEP.
- **DBS:** Dried blood spots will be prepared from finger pricks every three months in women on PrEP to evaluate adherence.
  - DBS cards will be prepared and stored following standard protocols and stored at -80°C for analysis at the end of the study with the clinical pharmacoanalytic laboratory of [name] at UCT. Using techniques developed by [name] at University of Colorado [16] adherence will be defined as red blood cells containing TDF-DP  $\geq 40\text{ng/dl}$  which is indicative of daily dosing [16]. As supplementary measures of PrEP adherence, we will use self-reported items that we will adapt from previous studies (including visual analogue scales as well as 3-day, 30-day and last visit recall questionnaires) (22-25), and pharmacy refill records to compare objective versus subjective measures and report on the effectiveness of each measure in correlation to the true measures of TDF-DP. We will determine final dosing and measures following reporting from ongoing PK studies of pregnant women on PrEP (e.g. Impaact 2009).
- Two self-collected vaginal swabs will be taken at enrollment and at 1-month visit. These will be stored at -80°C at University of Cape Town until processing for STI testing (at 2-3 weeks) and end of study

for bacterial and viral metagenomic sequencing. Briefly this will include microbial DNA extraction and shotgun metagenomic sequencing as performed previously by the [name] Lab (Brown, BP Biorxiv 2019).

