PrEP retention	# of women on PrEP who return for study visits (do not miss more than 1 visit) / total # of women in active cohort who are prescribed PrEP= proportion of women on PrEP who are retained in PrEP study	Electronic provider log (REDCap)	Daily, analysis weekly
PrEP adherence-subjective	# of women taking PrEP, who self-report taking their medication daily (& pill count to confirm this) during periods of sexual risk over time / total woman-time on PrEP in active cohort = PrEP adherence rate (subjective)	Electronic provider log (REDCap)	Daily, analysis weekly
PrEP adherence-objective	# of women taking PrEP who have >80% levels at >40ng/mL TDF-DP (indicating dosing in past 24 hours) at 3 rd trimester, delivery, and 6 weeks postpartum (and during sexual risk periods during that time) / total woman-time on PrEP in active cohort = PrEP adherence rate (objective)	Lab analysis of TDF-DP measures	Quarterly
Secondary Outcomes			
Predictors of attrition at key steps in the PrEP cascade	Individual, pill/study and disease specific predictors of attrition	Study survey	Study survey: Every study visit
HIV outcomes	HIV testing data: HIV-uninfected, HIV-positive for mother and child (if mother seroconverts)	Electronic provider log (REDCap)	Every visit
Health outcomes and adverse events	Any side-effects, creatinine, any negative maternal or neonatal outcomes (for mother and infant)	Electronic provider log (REDCap)	During routine lab tests and visits

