**Table 1. Study measures for PrEP-PP for AIM 1**

Primary Outcomes	Measurement	Source	Frequency
PrEP initiation	# of women who initiate PrEP over time / total # of women in active cohort = proportion of women who initiate PrEP	Electronic provider log (REDCap)	Quarterly
PrEP continuation	# of women on PrEP who return for study visits (do not miss more than 1 visit) / total # of women in active cohort who are prescribed PrEP= proportion of women on PrEP who continue in PrEP study	Electronic provider log (REDCap)	Quarterly
PrEP persistence (subjective)	# of women reporting taking PrEP in $\geq 5$ out of last 7 days or $\geq 25$ out of last 30 days (self-reported)/ total woman-time on PrEP in active cohort = PrEP persistence rate (subjective)	Electronic provider log (REDCap)	Quarterly
PrEP persistence (objective)	# of women taking PrEP who have $\geq 600$ fmol/punch (~7 doses/week) from DBS TDF-DP at 3rd trimester, delivery, and 6 weeks postpartum (and during sexual risk periods during that time) / total woman-time on PrEP in active cohort = PrEP persistence rate (objective)	Lab analysis of TDF-DP measures	Yearly and end of study
Secondary Outcomes			
Prevention effective persistence	4. # of women reporting adherence to PrEP (as per PrEP persistence subjective measure)/ total woman-time reporting sexual activity in past 30 days	Electronic provider log (REDCap)	Quarterly
	5. # of women having TDF-DP in DBS (as per PrEP persistence objective measure)/ total woman-time reporting sexual activity in past 30 days	Lab analysis of TDF-DP measures	Yearly and end of study

Prevention effective continuation	# of women who don't miss any PrEP study visits/ total woman time reporting sexual activity in prior visit	Electronic provider log (REDCap)	Quarterly
Predictors of attrition at key steps in the PrEP cascade	Individual, pill/study and disease specific predictors of PrEP initiation, continuation and persistence	Study CRFs and in-depth interviews (month 7 and12) (mixed methods)	End of study
Healthcare provider attitudes and knowledge about PrEP in pregnancy	Provider knowledge about PrEP and barriers/facilitators to PrEP prescription in ante and postnatal care	In-depth interviews	Year 1 of study
HIV outcomes	HIV testing data: HIV-uninfected, HIV incidence in mother and child (if mother seroconverts) compared by PrEP use/non-use	Electronic provider log (REDCap)	End of study

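### Self-reported and DBS persistence are cut at different dosing levels, so comparing them as defined would inflate apparent over-reporting of PrEP use

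*Combined protocol and SAP*

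**What the plan says.** - **The aim.** SAP section 1 states it twice. Under Statistical analysis considerations for Aims 1 and 2, persistence is measured "in participants through objective and subjective measures to evaluate agreement between the two measures, and the level of under- or over-reporting". Under Study measures: "We will measure persistence through objective and subjective measures to evaluate the agreement between the two measures, and the level of under- or over-reporting".
- **Self-report.** Study measures and SAP Table 1 count a woman as persistent if she reports at least 5 of the last 7 days or at least 25 of the last 30.
- **DBS.** The same places require at least 600 "fmol/punch (~7 doses/week) from DBS TDF-DP at 3rd trimester, delivery, and 6 weeks postpartum".
- **Carried forward.** SAP Table 1 uses both definitions again for prevention-effective persistence, over the same denominator: the number "of women reporting adherence to PrEP (as per PrEP persistence subjective measure)/ total woman-time reporting sexual activity in past 30 days" and the number "of women having TDF-DP in DBS (as per PrEP persistence objective measure)/ total woman-time reporting sexual activity in past 30 days".
- **Protocol.** Protocol Table 2 defines subjective adherence by women "who self-report taking their medication daily (& pill count to confirm this) during periods of sexual risk over time". Protocol section 5 describes its DBS level as one "which is indicative of daily dosing".
- **Not stated.** The SAP does not define an over-reporter, name the agreement statistic, say which cuts are compared, or give a DBS level for 5 to 6 doses a week.

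**The concern.** An over-reporter is naturally read as a woman who is positive on self-report and negative on DBS. With these definitions she need not have misreported anything. A woman who takes 5 or 6 doses a week and says so meets the self-report definition while taking less than the dosing the SAP attaches to the DBS definition. The mismatch runs in one direction only, towards apparent over-reporting.

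What is at stake is the answer to a question the SAP sets itself, namely how far self-report can be trusted in this population. The two prevention-effective rows of SAP Table 1 invite the same misreading, because any gap between them mixes reporting error with the difference in cuts.

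**Working it through.** **1. The two cuts on one scale.**
- 5 of 7 days = 5.0 doses a week.
- 25 of 30 days = 25/30 × 7 = 5.83 doses a week. The two recall rules are joined by *or*, so the second does not tighten the first.
- The DBS label is about 7 doses a week.
- The gap is 7 − 5 = 2, or 7 − 5.83 = 1.17, doses a week.

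**2. The plan's own figure.** The link from 600 fmol/punch to about 7 doses a week cannot be reproduced. The documents give no dose-concentration relation and no between-woman variability.

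**3. Illustration; every input is assumed.** All reports are true. DBS levels are lognormal with median proportional to weekly doses and CV 0.2, 0.3 or 0.5. The 600 cut lies at the 10th, 25th or 50th percentile (q) of true daily users. Women on 5 to 6 doses are 10%, 20% or 30% of users, half at each dose; 30% take 2.5 doses a week and the rest take 7. This gives 3 × 3 × 3 = 27 cells.

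With σ = √ln(1 + CV²), the chance that a woman on d doses a week falls below 600 is Φ(z_q + ln(7/d)/σ).

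*One cell in full: CV 0.3, q = 0.25, share 20%.*
- σ = √ln(1.09) = 0.294; z_q = −0.674.
- d = 5: Φ(−0.674 + 0.336/0.294) = 0.68. d = 6: Φ(−0.674 + 0.154/0.294) = 0.44. d = 7: 0.25.
- Truthful 5 to 6 dose women classed as over-reporters (gross): 0.10 × 0.681 + 0.10 × 0.441 = 11.2 points of all users.
- Same women with both cuts at 5 a week (illustrative DBS limit 600 × 5/7 = 429, not a proposed threshold): 0.10 × 0.25 + 0.10 × 0.098 = 3.5 points. Net excess: 11.2 − 3.5 = 7.7 points.
- Truthful daily women below 600: 0.50 × 0.25 = 12.5 points. Matching 7/7 days to 600 removes the 11.2 and leaves the 12.5.

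*All cells.*

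| Share at 5 to 6 doses | Gross, points | Net of a 5-a-week match, points |
|---|---|---|
| 10% | 2.3–8.7 | 1.5–5.4 |
| 20% | 4.5–17.4 | 3.1–10.8 |
| 30% | 6.8–26.1 | 4.6–16.2 |

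- The chance of falling below 600 is 0.28–0.96 at 5 doses, 0.17–0.78 at 6 and 0.10–0.50 at 7. The last range is the assumed percentile restated.
- Apparent over-reporting was higher with the unmatched cuts than with either match in 27 of 27 cells.
- Kappa with unmatched cuts was below both matched kappas in 17 cells, between them in 7 and above both in 3. At CV 0.2, 25th percentile, 20% share it was 0.50, against 0.92 matched at 5 and 0.63 matched at 7. At CV 0.5, 10th percentile, 20% share it was 0.65, against 0.59 and 0.48.
- After matching 7/7 days to 600, the remainder is (0.70 − share) × q, from 0.40 × 0.10 = 4 points to 0.60 × 0.50 = 30 points. It exceeds the amount removed in 15 of 27 cells.

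**The case against.** The strongest reply is that the error depends on a step the SAP never states.

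- **No explicit crossing.** No sentence says that the two binary cuts will be cross-classified. Where the SAP speaks of comparing alternate outcome definitions by measures of agreement, its example is self-report against pharmacy refill. No table shell holds a DBS row or an agreement row.
- **Graded measures are planned.** The SAP lists an execution ratio (doses reported or recorded over doses expected) and a semi-ordinal composite score from DBS. The protocol also plans to correlate subjective measures with TDF-DP.
- **Measures left open.** Protocol section 5 says: "We will determine final dosing and measures following reporting from ongoing PK studies of pregnant women on PrEP".
- **Limited reach.** DBS is the primary persistence analysis, and nothing says that the two prevention-effective rows will be subtracted.

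All of this is accurate, and it makes the point conditional. It does not remove it. The graded measures are not assigned to the over-reporting question, and the binary cuts are what the SAP gives as the definitions of subjective and objective persistence. Applying them as written produces the distortion.

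A reader might also infer that the SAP broke a clean daily-against-daily pairing in the protocol. The documents do not support that. Protocol Table 2's own DBS row asks for more than 80% of levels above a concentration that it ties to dosing in the past 24 hours, which is neither the daily-dosing label of section 5 nor a match to daily self-report.

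**Conclusion.** The concern holds in conditional form. If self-reported and DBS persistence are compared as the SAP defines them, truthful 5 to 6 dose users inflate apparent over-reporting. The direction follows from the SAP's own label and was the same in every assumed cell. The size, about 2 to 26 points gross, rests wholly on the assumed CV, percentile, proportionality and dose mix, and should not be quoted as an estimate for this cohort.

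Three stronger readings are not supported:
- **That agreement is understated.** Kappa moved both ways.
- **That the persistence results are biased.** The primary DBS estimate and the self-reported proportion do not depend on the comparison.
- **That matched cuts would isolate misreporting.** Biological spread alone leaves truthful daily users below the limit, and under the assumed inputs they can be the larger part of what remains.

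This should be settled before the agreement analysis is run. It does not threaten the primary analysis.

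**What to change.** Add to the SAP:
1. Define over-reporting, and state that agreement is assessed at matched dosing levels. The main comparison is zero missed days (7/7 or 30/30) against the DBS level labelled about 7 doses a week.
2. Compare at least 5 of 7 days with a DBS level for that dosing only if a named calibration source, covering pregnancy and postpartum, supplies one.
3. Alternatively, compare ordered self-report dose bands with the semi-ordinal DBS score already planned, using weighted kappa.
4. State that remaining discordance will not be read as misreporting. With the 7/7 match, 5 to 6 dose women above 600 also move to the under-reporting cell, so both off-diagonal cells need this caution.

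Keep raw day counts. The SAP Part 3 template has zero-missed rows for both windows, but its 1–3 missed-days bin straddles the 5-of-7 cut. Confirm that the 7-day item was collected: the protocol's Survey measures list 3-day and 1-month recall, while the SAP lists 7-day and 30-day. If it was not, use the 30-day count.

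The cost is some SAP wording, a few cross-tabulations and one added agreement table shell; the calibration source is needed only for item 2.

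Separately, the DBS threshold and matrix are given as 40 ng/dl (protocol section 5), 40 ng/mL (protocol Table 2), and 600 fmol/punch alongside a mention of plasma (SAP Study measures). These passages must be reconciled; the documents do not show which is right.
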